5.1 Patient evaluability and replacement

The trial will be assessed on a modified intention-to-treat basis. Patients who are not evaluable for the primary endpoint may be replaced at the TMGs discretion, this includes:

- Patients who receive fewer than 3 doses of xentuzumab e.g. due to early withdrawal
- Patients who for any reason do not have their planned standard of care prostatectomy
- Patients whose prostatectomy reveals predominantly neuroendocrine/small cell cancer
- Patients from whom diagnostic biopsy or surgical specimens were not taken or were of insufficient quantity or quality for analysis.
- Patients who do not receive their planned standard of care prostatectomy within 6 days of their final dose of xentuzumab.

If patients miss a dose(s) for unavoidable reasons (e.g. participants with covid infection or unable to attend for treatment in the scheduled visit window) they can remain on the trial provided they resume weekly dosing with the final dose of xentuzumab within 6 days of surgery.
All participants who receive one or more doses of xentuzumab will be evaluable for safety analysis.

As noted above, patients withdrawing early after one or more doses of xentuzumab, irrespective of their stage in the trial, will undergo evaluations on the day before surgery.

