7.3 Duration of treatment

Patients should receive 4 weekly doses of xentuzumab on days 1, 8, 15 and 22, prior to prostatectomy. In the event that surgery takes place later than day 29 a 5th dose should be administered on day 29. If surgery is further delayed up to 10 doses in total can be administered. In the event that surgery takes place prior to day 22, it is acceptable for patients to have only 3 doses. The final dose of xentuzumab should be within 6 days of the scheduled prostatectomy. A maximum of 10 doses of xentuzumab can be given.

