**Table 1: Estimand-to-analysis table template**

**Primary Objective:** Assess the amount of IGF pathway inhibition induced by xentuzumab

**Estimand:** The amount of IGF-1 blockade induced by xentuzumab measured through automated immunohistochemistry (IHC) analysis of IGF-1 receptor activation (phospho-IGF-1R) and downstream activation marker phospho-S6.

**Treatment:** Xentuzumab infusion (1000mg), once weekly for a minimum of 4 weeks

Estimand	Analysis
Target population	Analysis set
Men ≥ 18 years old with prostate cancer who are scheduled for radical prostatectomy.	All participants who meet trial eligibility criteria and initiate treatment.
Variable	Outcome measure
H-Score or % of positively stained cells for phospho-IGF-1R and phospho-S6 as measured by IHC.	Statistical significance of the difference between IGF1 axis activity in PRE treatment and POST treatment samples.  All participants who have sufficient material in the diagnostic (PRE-treatment) and in theatre (POST-treatment) biopsy cores for IHC analysis will be included, provided intercurrent events have not affected their ability to meet trial eligibility criteria.
Handling of intercurrent events	Handling of missing data
Intercurrent events which prevent the patient from having in theatre (POST-treatment) biopsy cores available for IHC analysis after at least 4 doses of xentuzumab will preclude the patient from analysis of the primary endpoint. This does not fall under the	Missing data will not be imputed. Patients whose samples are not sufficient to provide a score at baseline and after treatment will be excluded from the primary endpoint analysis. For other endpoints/analyses, Chief Investigator  Sensitivity analysis: NA, data will not be imputed.

typical handling of intercurrent events due to the single arm design of this trial.

Intercurrent events that do not prevent the patient from having in theatre (POST-treatment) biopsy cores available for IHC analysis, and would not affect the patient's trial eligibility, will be assessed by the Chief Investigator.

Population-level summary measure	Analysis approach

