## 6.2 Analysis Methods

*For each primary and secondary outcome, describe what analysis methods will be used and how treatment effects will be presented (e.g. tabular and graphically- Cross-reference to the SAP – Data definitions and Tables). Detail which analysis population will be analysed. Detail any adjustment for covariates. Describe any methods to be used to check statistical assumptions and detail alternative methods if the assumptions do not hold, e.g. normality, proportional hazards. Where multiple analyses are planned, clearly distinguish which analysis will be the principal analysis, on which the outcome of the trial will be assessed, and which will be*

*supporting analyses to aid interpretation. Details of sensitivity analyses and multiple imputation should be detailed either under each key outcome analysis where applicable or in separate sections (5.3 and 5.4)*

The primary endpoint (i.e. the amount of IGF pathway inhibition induced by xentuzumab)s will be presented as in WINGMEN\_DataDefinitions&Tables Section 4.3.1, Figure 1, and Table 6 and analysed as described in Section 4 above.

The trial will be assessed on a modified intention-to-treat basis. Patients who are not evaluable for the primary endpoint may be replaced at the discretion of the Trial Management Group; including:

- Patients who receive fewer than 3 doses of xentuzumab (e.g. due to early withdrawal).
- Patients who for any reason do not have their planned standard of care prostatectomy.
- Patients whose prostatectomy reveals predominantly neuroendocrine/small cell cancer.
- Patients from whom diagnostic biopsy or surgical specimens were not taken or were of insufficient quantity or quality for analysis.
- Patients who do not receive their planned standard of care prostatectomy within 6 days of their final dose of xentuzumab.

All participants who receive one or more doses of xentuzumab will be evaluable for safety analysis, and patients withdrawing early after one or more doses of xentuzumab, irrespective of their stage in the trial, will undergo evaluations on the day before surgery.

The secondary outcomes relate to safety and feasibility of treatment and will be presented as described in Section 4.1.2 and WINGMEN\_DataDefinitions&Tables Section 4.3.2 and Tables 7 and 8. The data will be tabulated and statistical analyses will not be conducted on these results.

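### SAP Table 1 ties the primary analysis to at least four doses, while SAP 6.2 and Protocol 5.1 treat three doses with surgery within six days as evaluable

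*SAP*

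**What the plan says.** **Four doses.** SAP Table 1 defines treatment as a weekly infusion, "once weekly for a minimum of 4 weeks". Its intercurrent-event cell says that an event leaving no in-theatre cores "after at least 4 doses of xentuzumab will preclude the patient from analysis of the primary endpoint". Events that leave cores available and do not affect eligibility "will be assessed by the Chief Investigator"; no criteria or timing are given.

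**No dose minimum, same table.** The outcome-measure cell of Table 1 includes everyone with enough paired material whose eligibility has not been affected. The analysis-set cell asks only for eligibility and a start of treatment.

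**Three doses.** SAP 6.2 lists who is not evaluable for the primary endpoint. The list includes "Patients who receive fewer than 3 doses of xentuzumab (e.g. due to early withdrawal" and "Patients who do not receive their planned standard of care prostatectomy within 6 days of their final dose of xentuzumab". It also covers no prostatectomy, predominantly neuroendocrine or small cell histology, and missing or inadequate specimens. Protocol 5.1 gives the same list. Protocol 7.3 adds: "In the event that surgery takes place prior to day 22, it is acceptable for patients to have only 3 doses". Protocol 1.2 calls three treatments sufficient when surgery falls before day 29. For patients who miss doses unavoidably, Protocol 5.1 and 7.4 say "they can remain on the trial provided they resume weekly dosing with the final dose of xentuzumab within 6 days of surgery".

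**General wording.** Protocol 14.1 admits patients with both pre- and post-treatment data, whether or not treatment was completed. SAP 5.2 keeps the samples of early withdrawers for analysis, with consent. Neither names the primary endpoint.

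**The concern.** The primary analysis is a paired comparison in a trial planned for 20 to 30 men, so who is in the set matters. Two analysts working from this SAP could form different sets from the same patients, one applying the four-dose cell of Table 1 and the other the list in 6.2. The sets would differ by exposure (number of doses, gap from last dose to surgery) and not at random. The estimated pathway inhibition could therefore differ; the documents do not show in which direction.

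The discretionary route adds to this. Remaining intercurrent events go to the Chief Investigator without a rule or a deadline, and SAP 3.5 says that some laboratory members know which samples are pre- and which post-treatment.

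No planned analysis compares the candidate sets. SAP 6.5 rules out supplementary analyses of the primary endpoint, and SAP 6.3 deals with assay controls and spare material.

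**Working it through.** **1. The plan's own figure.** Protocol 13.1 and SAP 3.2 give effect size d = 0.68, two-tailed 5%, 80% power, Wilcoxon signed rank: 20 pairs (16 one-tailed). Take an effective sample size m = n × 3/π and a noncentral t with m − 1 degrees of freedom and noncentrality d√m. For n = 20, m = 60/π = 19.10 and d√m = 0.68 × 4.370 = 2.97, which gives power 80.3%. For n = 19 it is 78.0%, so 20 is the smallest adequate number. One-tailed, 16 pairs give 81.2%. Both stated figures reproduce; the conflict does not make the sample size wrong.

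**2. The rules applied to patient types.** All types have adequate paired specimens; days are nominal.

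| Patient | Protocol 5.1 / SAP 6.2 | Table 1, four-dose cell | Table 1, outcome cell | Protocol 14.1 |
|---|---|---|---|---|
| A. Doses days 1, 8, 15; surgery days 16–21 (gap 16−15 = 1 to 21−15 = 6) | Evaluable | Out | In | In |
| B. One missed dose: days 1, 8, 22; surgery days 23–28 (gap 23−22 = 1 to 28−22 = 6) | Evaluable | Out | In | In |
| C. Four or more doses, gap over 6 days | Not evaluable | Not barred; Chief Investigator | In | In |
| D. One or two doses | Not evaluable | Out | In | In |
| E. Four or more doses, gap within 6 days, predominantly neuroendocrine/small cell | Not evaluable | Not barred by dose; no stated rule | In, if eligibility is held unaffected | In |

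The outcome-cell entries for A to D assume that eligibility is unaffected. A and B carry the point: the protocol allows them, SAP 6.2 counts them, and the four-dose cell removes them. Surgery on days 16–21 (A) lies outside the day 24–42 window in the schedule of events, although Protocol 7.3 permits it. For B, surgery on days 24–28 lies inside that window. C and E show that changing four to three would not be enough, because Table 1 also lacks the six-day limit and the histology exclusion.

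**3. Scale, for orientation only.** The number of three-dose men is not given, so a range is assumed. Two-tailed Wilcoxon, d = 0.68:

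- From 20 pairs: none dropped 80.3%, one 78.0%, two 75.5%, three 72.7%, four 69.7%.
- From 24 pairs (87.5%): power stays at or above 80% with up to 24 − 20 = 4 dropped.
- From 30 pairs (about 94%): the same holds with up to 30 − 20 = 10 dropped.

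The SAP's first-choice paired t-test is slightly more forgiving: 82.2% with 20 pairs and 80.0% with 19.

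**The case against.** *The lists in Protocol 5.1 and SAP 6.2 are replacement rules.* They are, and they accept three doses only by implication. But they are framed as lists of who is not evaluable for the primary endpoint, and Protocol 1.2 and 7.3 accept three doses directly.

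*Table 1 does not clearly exclude three-dose men.* This stands in part. Only the four-dose cell excludes them; the outcome-measure cell would keep them. That makes Table 1 ambiguous and does not settle the rule.

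*The Data Definitions document may settle it.* SAP 4.2 sends the analysis populations to Section 3 of that document, and SAP 1 says the two are read together. It may well define the set. Table 1 and SAP 6.2 would still disagree.

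*Few patients can be affected.* This is plausible. The amendment history says protocol version 2.0 added three-cycle evaluability and the allowance for omitted doses. SAP 1.2 dates that version 21 November 2022, and SAP 3.4.4 says recruitment was complete by Q1 2023, so these routes were formally open for about four months at most. Few or no men may fall into types A and B.

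*The SAP has safeguards.* SAP 7 has an independent statistician repeat the primary analysis, and SAP 5.5 records delayed cycles with reasons. So it would be wrong to infer that nothing could bring the problem to light. These steps might expose a disagreement, but they do not say which set is right or what the other set would give.

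*Four doses may be intended.* A reader might take the wording for a leftover from before the amendment. The documents do not show that: this is SAP version 1.0, it cites protocol 2.0, and it uses four doses again in 4.1.2, 5.5 and Table 3. If four was meant, SAP 6.2 is wrong and the departure from Protocol 5.1 needs stating. Either way the text has to change.

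**Conclusion.** The point holds as an inconsistency in the current text: the four-dose cell and treatment definition of SAP Table 1 against SAP 6.2 and Protocol 5.1, with a second conflict inside Table 1. It should be corrected because it concerns the set on which the primary result rests.

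Two stronger readings go too far. A reader might infer that Protocol 14.1 is a third, equal rule for the primary set. Its wording is general, while Protocol 5.1 is specific to the primary endpoint; what can be said is that the relation between them is not stated. A reader might also infer from the power figures that the trial is underpowered. That would need the number of three-dose men and the number of usable pairs, and the documents give neither.

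Confidence is high in the textual conflict. It is lower in the practical consequence, which depends on Data Definitions Section 3 and on how many patients had exactly three doses.

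**What to change.** Amend the SAP before paired results are seen or, if they have been seen, say so in the amendment.

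1. In Table 1, replace the four-dose condition and the four-week minimum with the full list of Protocol 5.1 and SAP 6.2: at least three doses; prostatectomy performed within six days of the final dose; not predominantly neuroendocrine or small cell cancer; adequate paired specimens. Make the outcome-measure cell and Data Definitions Section 3 say the same.
2. State that this rule, and not Protocol 14.1 or SAP 5.2, defines the primary set.
3. Reconcile the four-dose wording in SAP 4.1.2, 5.5 and Table 3 with Protocol 3 and 7.3. For the feasibility endpoint, Protocol 3 counts surgery on schedule after three doses, while SAP Table 3 counts surgery within seven days of the fourth.
4. Record each Chief Investigator decision on other intercurrent events, with its reason, before results are seen.

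Optional: report all complete pairs, as in Protocol 14.1, as one labelled supportive analysis, with a listing of each patient's dose count and gap from final dose to surgery. SAP 6.5 would need to allow it.

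Cost: one SAP amendment and, if the option is taken, one listing and one supportive p-value. No new data are needed: recruitment is complete, and dose and surgery dates should already be on record.

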### 3 STUDY METHODS

#### 3.1 Trial Design/framework

This is a phase 0 'window of opportunity' study testing whether IGF neutralising antibody xentuzumab blocks IGF signalling and markers of aggressive tumour growth in men with localised prostate cancer scheduled for radical prostatectomy. Three factors influenced the trial design, and in particular the absence of a control arm. Firstly, trial design was informed by views of patients scheduled for prostatectomy. Men showing interest in the trial expressed the view that they would be less likely to participate in a trial randomising between treatment and control arms, because if they did take part, given the inconvenience of assessments and additional blood tests, they would want to receive the treatment. Other factors included the increased cost to Prostate Cancer UK of adding a control arm, doubling the trial size and cost, and the fact that the strength of a pre-operative windows study is the intra-patient pre/post treatment comparison.

#### 3.2 Sample Size

*Details of the sample size for primary outcomes and any co-primary or key secondary outcomes (if applicable), including treatment effect, power, levels of statistical significance (one-tailed or two-tailed), clinical relevance and justification.*

Trial size calculations were initially based on analysis of phospho-AKT immunohistochemistry in tumours of mice following 3 weeks treatment with xentuzumab (Figure 6G in [2]). Compared with control treatment, the reduction in phospho-AKT signal induced by xentuzumab indicates an effect size of 2.35. In anticipation of a reduced effect in a heterogeneous clinical population, calculations are based on a more conservative estimate of an effect size of 0.6. Recruitment of 24 patients, giving 24 matched pairs of tissue (diagnostic biopsy and in-theatre biopsy), will enable reduction in phospho-AKT (or downstream target) (measured by H-Score or

percentage of positively stained cells) to be significant at the 5% level with 80% power. We will recruit 30 patients in case some prostate biopsies are inadequate or unsuitable for translational studies.

These calculations were checked against preliminary clinical data suggesting association of high serum IGF-1 with increased IGF-1R content of malignant but not benign prostatic epithelium in a radical prostatectomy cohort of 139 patients with T1-T3a prostate cancer (Table 2). Supporting the proposed sample size calculated above, recruitment of 25 patients will enable a 2-point reduction in IGF-1R (measured by H-Score or percentage of positively stained cells) to be significant at the 5% level with 80% power (with within-person standard deviation of 3.5). Simulations from clinical data indicate that weekly dosing of 1000mg xentuzumab reduces mean free IGF-1 by >90% and mean free IGF-2 by 64% relative to pre-treatment. This suggests that the proposed intervention will have a biological effect at least as great as the difference in circulating IGF-1 levels in the radical prostatectomy cohort.

Sample size calculations were repeated in October 2022 based on newly acquired preclinical data quantifying the amount of IGF axis pathway inhibition achieved by xentuzumab. This equates to the WINGMEN trial primary endpoint: the amount of IGF axis pathway inhibition. In a preclinical prostate cancer model, xentuzumab suppressed IGF-1R phosphorylation (pIGF-1R) with an effect size of 0.68 (G\*Power v3.1). Using Wilcoxon signed rank test (matched pairs, 2-tailed), recruitment of 20 patients (20 matched pre/post-treatment pairs) will be significant at the 5% level with 80% power. Using a one-tailed test, based on the hypothesis that xentuzumab will reduce pIGF-1R, we will need 16 patients (16 matched pairs of tissue). Therefore, we aimed to recruit 20-30 patients in case some prostate biopsies are inadequate or unsuitable for translational studies.

	n	Median serum IGF-1 nmol/l		n	Median serum IGF-1 nmol/l	p value
Benign epithelium						
IGF-1R score ≤ 10	77	16.54	IGF-1R score > 10	60	16.68	p=0.871
Malignant epithelium						
IGF-1R score ≤ 14	79	15.58	IGF-1R score > 14	60	17.07	p=0.038

**Table 2. Serum IGF-1 associates with IGF-1R immunoreactive score in malignant prostate epithelium.** Immunoreactive scores (calculated as described in [3] were divided by the median values. IGF-1R scores were generally higher in malignant epithelium, consistent with our earlier report of IGF-1R overexpression in prostate cancer [4], hence cut point of 14 in malignant epithelium vs 10 in benign epithelium. NB Two samples had no benign epithelium in the scored sections ([name], [name], [name], unpublished).

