## 4 STATISTICAL PRINCIPLES

### 4.1 Statistical Significance and Multiple Testing

*If the analysis is under a conventional (statistical hypothesis testing approach), state the level of statistical significance and the confidence intervals to be reported. Acknowledgement of the issue of multiple testing (if applicable), together with the rationale of the intention to formally or informally adjust for multiplicity. If no adjustment planned this will be stated. State which outcomes will be adjusted for multiplicity (if applicable).*

Initial analysis will assess variables for normal distribution using the Shapiro-Wilk test. All tests will be 2-tailed and  $p \leq 0.05$  will be accepted as statistically significant.

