## 6.1 Outcome Definitions

*Provide a simple list of all primary and secondary outcomes, together with time-points at which they are collected, with full details of definitions, and how these outcome variables will be generated and reported as provided in SAP - Data Definitions and Tables which should be cross-referenced.*

	Objectives	Endpoints
Primary endpoint	Assess the amount of IGF pathway inhibition induced by xentuzumab	Phospho-IGF-1R and phospho-S6 immunohistochemistry on tissue from biopsy and prostatectomy
Secondary endpoints	1. Feasibility of treatment in pre-operative setting 2. Assess safety and tolerability of xentuzumab administered in the pre-prostatectomy setting	1. Number of patients whose radical prostatectomy is performed within 7 days of the 4 th dose of xentuzumab (patients can receive up to 10 doses of xentuzumab if surgery is delayed) 2. Treatment-related adverse events scored using NCI-CTCAE v5.0
Tertiary/exploratory endpoints	1. Assess change in PSA following administration of xentuzumab in the pre-prostatectomy setting 2. Assess changes in tissue markers following administration of xentuzumab in the pre-prostatectomy setting 3. Assess changes in circulating markers following administration of xentuzumab in the pre-prostatectomy setting 4. Correlate changes in IGF-1R expression, IGF axis activity with cancer profile which may include mutation analysis, gene expression and phosphoproteomic profile	1. Change in serum PSA 2. Changes by IHC on FFPE tissues in tissue markers (e.g. Ki67 index, IGF-1R, RRM2, CD31, immune markers: PD-L1, CD4, CD8, FoxP3) 3. Changes in circulating markers of endocrine response to IGF blockade (e.g. IGF-1, insulin, IGFBPs, circulating IGF bioactivity, plasma metabolomic profile) 4. Tumour profiling (e.g. gene mutation panel, IHC for PTEN, FISH for TMPRSS2-ERG, transcriptional and phospho-proteomic profile of index tumour)

Table 3. Definition of WINGMEN outcomes.

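### The 20-pair sizing covers phospho-IGF-1R only, but the primary endpoint tests two markers with no rule for combining them, so either the 5% level or the 80% power is lost once both are used

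*SAP*

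**What the plan says.** SAP 3.2 repeats the sample size calculation in October 2022. In a preclinical model, "xentuzumab suppressed IGF-1R phosphorylation (pIGF-1R) with an effect size of 0.68". With a two-tailed Wilcoxon signed-rank test, "recruitment of 20 patients (20 matched pre/post-treatment pairs) will be significant at the 5% level with 80% power"; a one-tailed version needs 16 pairs. The SAP introduces this calculation with the sentence "This equates to the WINGMEN trial primary endpoint: the amount of IGF axis pathway inhibition". Protocol 13.1 gives the same numbers without that sentence.

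The primary endpoint in SAP 6.1 (Table 3) is "Phospho-IGF-1R and phospho-S6 immunohistochemistry on tissue from biopsy and prostatectomy". SAP 4.1.1 compares PRE and POST scores by paired t-test, or by signed-rank test if the differences are not normal. Under SAP 4.1 all tests are two-tailed and p ≤ 0.05 "will be accepted as statistically significant". SAP Table 1 makes statistical significance the population-level summary for the primary objective.

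Neither SAP 4.1 nor 4.1.1 gives an order of testing, an either/both rule or an adjustment for the two markers. The template text in SAP 4.1 asks for the multiplicity position, including a statement if there is no adjustment. Adjustment is specified for metabolomics (4.1.4) and RNA-seq (4.1.5). SAP 6 adds that, depending on the assessment of the HALO results, percentage change in one marker or in both may be used to quantify inhibition. Protocol 14 also gives no combination rule.

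SAP 3.2 also keeps an older calculation, the only one that reaches a downstream marker: "Recruitment of 24 patients, giving 24 matched pairs of tissue (diagnostic biopsy and in-theatre biopsy), will enable reduction in phospho-AKT (or downstream target"). That calculation assumes 0.6 for the effect and claims 80% power at a 5% level.

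**The concern.** The sizing describes a trial with one primary test, but the analysis plan describes two. When significance is itself the primary result, two p-values need a stated route to one conclusion. Without it, the power and error rate of the two-marker endpoint are undefined, and a reader who takes the sizing as describing that endpoint is misled whichever two-marker rule is later applied.

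The open choice in SAP 6 adds to this. If the marker that represents inhibition is settled after the results are assessed, the analysis can drift towards whichever marker moved.

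**Working it through.** **Inputs from the documents.** phospho-IGF-1R effect 0.68; two-sided 0.05; 20 pairs; 80% power; downstream-marker planning effect 0.6 with 24 pairs (all SAP 3.2). Test: paired t or Wilcoxon signed-rank (SAP 4.1.1).

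**Assumptions.** The documents give no correlation between the two markers' changes, so it is varied from 0 to 0.9. They give no effect for phospho-S6 by name, so 0.68 and 0.60 are both used. Differences are taken as normal.

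**1. Reproduce the plan's figure.** For the Wilcoxon test, multiply n by its relative efficiency 3/π = 0.955 and use the noncentral t.
- Effective n = 20 × 0.955 = 19.10; noncentrality = 0.68 × √19.10 = 2.97; critical t = 2.10; power = 0.803.
- One-sided with 16 pairs: 0.812. Paired t with 20 pairs: 0.822.

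The 20 and 16 pairs are correct for phospho-IGF-1R.

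**2. phospho-S6 alone, if its effect is 0.6.**
- 20 pairs: noncentrality = 0.6 × √19.10 = 2.62; power = 0.699 (Wilcoxon) or 0.721 (paired t).
- 80% power needs 24 pairs by paired t (0.804) or 25 by Wilcoxon (0.801; 24 pairs give 0.784).

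**3. Two markers at 20 pairs.** With independent markers:
- Either marker, no effect on either: 1 − 0.95² = 9.75%.
- Both markers: 0.803 × 0.803 = 0.645 (both 0.68), or 0.803 × 0.699 = 0.561 (0.68 and 0.60).

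With correlation, by simulation (60,000 replicates per setting, bivariate normal differences, exact signed-rank null). Entries are Wilcoxon / paired t, in %:

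| Correlation | Either: false positives | Either: power, both 0.68 | Both: power, both 0.68 | Both: power, 0.68 and 0.60 |
|---|---|---|---|---|
| 0 | 9.6 / 9.9 | 96.0 / 96.9 | 64.3 / 67.8 | 56.1 / 59.3 |
| 0.5 | 8.8 / 9.1 | 92.0 / 93.0 | 68.2 / 71.5 | 61.3 / 64.2 |
| 0.9 | 7.1 / 7.1 | 86.0 / 87.1 | 75.0 / 77.5 | 67.4 / 69.9 |

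Under the both-markers rule a false claim requires at least one marker with no effect to reach p ≤ 0.05, so the error cannot exceed 5%.

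**4. More pairs.** Both-markers power over correlation 0–0.9 and either test (40,000 replicates per setting):

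| Evaluable pairs | Both 0.68 | 0.68 and 0.60 |
|---|---|---|
| 24 | 77–85% | 69–79% |
| 28 | 85–91% | 78–86% |
| 30 | 88–93% | 82–88% |

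The either-marker false-positive rate stays at about 7–10% at 24, 28 and 30 pairs, because it depends on the number of tests and their correlation, not on n.

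**The case against.** The strongest defence has four parts.

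- **The sized marker is named.** SAP 3.2 says openly that the effect is for phospho-IGF-1R, and the equating sentence can be read as being about the biological quantity, not about power. That reading is possible. But the sentence sits inside the sample size justification, and nothing there says the 80% excludes phospho-S6.
- **Twenty is the bottom of the range.** The SAP aims for 20–30, Protocol 2 says thirty, and SAP 6.2 refers to 30. This stands for power: under a both-markers rule the loss shrinks or disappears by 24–28 evaluable pairs. However, the surplus is there to cover unsuitable biopsies, the evaluable number is not given, and extra pairs do nothing for the error rate under an either-marker rule.
- **Recruitment is over.** SAP 3.4.4 says it was complete by Q1 2023, so SAP 3.2 can no longer change enrolment. That is true, but the decision rule still determines what the results may claim.
- **A rule may exist elsewhere.** The Data Definitions and Tables document, which is to be read with the SAP, is not available here. SAP 4.1 is nevertheless where its own template asks for the rule.

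A reader might go further and infer that neither the 80% power nor the 5% level holds. The documents do not support that, because the two fail under different rules. An either-marker rule loses the 5% level but has more than 80% power; a both-markers rule loses power at 20 pairs but keeps the 5% level.

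**Conclusion.** The point holds in this form: the 20-pair calculation is correct for phospho-IGF-1R, the primary endpoint has two markers, and no rule connects them. One stated property is lost under each two-marker rule. If either marker suffices, false positives run at about 7–10% against 5%. If both are required, power at 20 pairs is about 56–70% (effects 0.68 and 0.60) or 64–78% (both 0.68) against 80%.

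Phospho-S6 alone has about 70–72% power at 20 pairs if its effect is 0.6. That 0.6 is a deliberately cautious planning figure for phospho-AKT or a downstream target, reduced from an observed 2.35. It is not an estimate for phospho-S6.

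It does not follow that the trial as run is underpowered: that depends on the evaluable number, the correlation and the phospho-S6 effect, none of which the documents give. For a single-arm Phase 0 study this should be corrected, and the correction is small.

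**What to change.** - **SAP 4.1.1.** Test phospho-IGF-1R first at two-sided 0.05. Test phospho-S6 at two-sided 0.05 only if the first is significant; otherwise report it descriptively. This holds the overall error at 5% for any correlation and leaves the 80% intact for the marker that was sized.
- **SAP 6.** Remove the results-dependent choice. State that percentage change is reported for both markers, with phospho-IGF-1R as the lead measure.
- **SAP 3.2.** Replace the sentence that equates the calculation with the primary endpoint. Say that 20 pairs give 80% power for phospho-IGF-1R and, at an assumed effect of 0.6, about 70% for phospho-S6 tested alone (24–25 pairs for 80%).
- **Timing.** The documents do not say whether the primary IHC results have been seen. If they have, label the change as made after data review.

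The cost is a few sentences, with no patients or assays. The downside is that phospho-S6 cannot support a formal claim if phospho-IGF-1R is not significant. Other rules would also close the gap, for example requiring both markers, or 0.025 for each (about 70% power per marker at 20 pairs and 25 pairs for 80%, at effect 0.68 by Wilcoxon). The fixed order is preferred because it matches the sizing already done.
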